# 5.3.6 At home procedures (Days 21-28; 35-42)

Participants will complete a daily diary including the CIPN Symptom Inventory and consumed rescue analgesic medication (i.e., acetaminophen (Tylenol) or NSAIDs). They will be asked to complete it before bedtime when they are not wearing the device during weeks 4 and 6.

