# 5.3.8 End of Study Visit (Day 42; +/- 5 days) (approximately 1 hour and 15 minutes)

All participants will complete the patient-reported outcome measures, balance tests, conditioned pain modulation test, and lower limb sensation test. The coordinator will also review the list of medications that the participant reported using for CIPN at the beginning of the study and ask the participant if they changed dosages of any of the medications. Any changes will be recorded in the Changes in concomitant analgesic medications form. The coordinator will ask the participant for their device and open the Quell App to ensure final data transfer to the cloud. The data will then be downloaded by the device manufacturer and sent to the Research Base. If the participant does not come to the Week 6 visit, the coordinator will call them up to 3 times to try to reschedule the visit. The rescheduled visit can occur up to 1 month after the date of the 6-week visit. If the participant agrees to come back in, they will be encouraged to keep using the device until the rescheduled visit date.

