including hot/burning pain, sharp/shooting pain, tingling, cramping, and numbness (**Daily Diary**). The participant will also be asked to rate these symptoms, while thinking about the past week at each visit (**CIPN Symptom Inventory – week recall**). NRS scores and their composites are frequently used to assess symptoms in cancer and pain patients (e.g., MD Anderson Symptom Inventory [58]). Furthermore, the daily diary of a single-item 0–10 NRS for pain intensity is commonly used as the basis for approval of chronic pain medications by the FDA.[59] The symptom diaries will instruct the participants to focus on the symptoms in their lower limbs and perform ratings in the evening before bed while considering the past day. Based on our preliminary data, a composite measure of these symptoms in the lower limbs may be particularly responsive to the TENS intervention. Our pilot data also indicate that the outcome that is based on the average of the weekly symptom ratings has considerably less variability than the single day ratings (i.e., standard deviation of 4.6 vs 5.7) and could significantly decrease the sample size requirement of a future trial. **(5 items)** 

(3) Treatment-Induced Neuropathy Assessment Scale (TNAS). The TNAS is a PRO that assesses symptoms and functional interference from CIPN in 2 separate domains. It was developed and refined in multiple stages, including interviews with patients and clinicians to develop content valid items, and cognitive debriefing to assess the understandability of the items. It has acceptable reliability and sensitivity to change.[60, 61] (9 items)

**CIPN interference.** CIPN interference in general activity, mood, walking, normal work, relationships, sleep, and enjoyment of life will be measured using the **CIPN Interference Questionnaire**, which uses 0 – 10 NRSs [0 = does not interfere, 10 = completely interferes] adapted from the Brief Pain Inventory (BPI). [62] The BPI is a well-established measure used to assess chronic pain in clinical trials and clinically. **(7 items)** 

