# 9.2 Schedule of Data Collection

#### Table 10. Forms to Be Kept

FORMS	Screening	Baseline	Week 6		
Participant Forms (paper)					
On-Study		Х			
Expectation Questionnaire		Х			
EORTC CIPN20		Х	Х		
Daily Diary (CIPN symptoms / rescue medication usage)*		Х	Х		
CIPN Symptom Inventory – week recall	Х	Х	Х		
TNAS		Х	Х		
PROMIS 1		Х	Х		
PROMIS 2		Х	Х		

PROMIS 3		Х	Х
CIPN Interference Questionnaire		Х	Х
General Impression of Neuropathy			Х
General Impression of Activity			х
Blinding Questionnaire			Х
Qualitative Feedback Questionnaire			Х
Coordinator Forms (REDCap  , paper  )			•
Eligibility checklist (Medical Record, Clinician-reported, and Patient-reported items) 	х		
Consent form 	Х		
Clinical record information form 	Х		
TENS Device Settings form 		Х	
CPM data collection form 	X	Х	Х
SPPB Balance form 		Х	Х
Lower-limb sensation threshold data collection form 	X	Х	Х
Coordinator blinding question 			Х
Changes in concomitant analgesic medications form 			Х
Adverse Event (AE) Form 1**			Х
Screening log completed for patients who a Submit chemotherapy treatment notes from	are approached, l n participant's me	but not consen edical record at	ted Screening

Telephone Contact Sheet to be completed with each phone call

\* Daily diary will be completed during the week between the Screening and Baseline visits (collected at the Baseline Visit) and during Weeks 4 (i.e., day 21 - 28) and 6 (i.e., day 35 - 42) (collected at 6 Week visit).

\*\* Adverse Events are also assessed during Week 1, 3, 5 phone calls

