**10.5** Secondary Analyses. ANCOVA analyses as in the primary analysis will be used for individual symptoms (i.e., hot/burning and sharp/shooting pain, numbness, tingling, and cramping (0 - 10 NRS)). For each of the symptoms, baseline and Week 6 scores will be calculated as the mean of weekly daily diary scores during the week between Screening and Baseline and Week 6, respectively.

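### An in-window Week 6 visit on Days 37-41 cuts the Week 6 diary to 2-6 evenings, and a missed visit shifts or loses the Week 6 CIPN20 and both on-treatment diaries, because no off-visit return route is stated (minor)

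*Combined protocol and SAP*

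**What the plan says.** **Visit.** The heading of Section 5.3.8 reads "End of Study Visit (Day 42; +/- 5 days", that is, Days 37 to 47. All Week 6 patient-reported outcomes are completed there. After a missed visit the only stated step is up to three calls to rebook: "The rescheduled visit can occur up to 1 month after the date of the 6-week visit", and in the meantime "they will be encouraged to keep using the device until the rescheduled visit date". Section 7.1 places the primary CIPN20 endpoint after six weeks of device use, and Section 5.2 prescribes daily wear for six weeks.

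**Diary.** Section 5.3.6 fixes the on-treatment diaries at Days 21-28 and 35-42: "They will be asked to complete it before bedtime when they are not wearing the device during weeks 4 and 6". Table 10 (Section 9.2) lists the CIPN20 and the diary as paper participant forms. Its footnote has the Week 4 diary come back together with that of Week "6 (i.e., day 35 - 42) (collected at 6 Week visit".

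**Analysis.** Section 10.5 scores each symptom as the "mean of weekly daily diary scores during the week between Screening and Baseline and Week 6, respectively" and states no minimum number of entries. Section 10.4 classifies analgesic use by whether the number of days on acetaminophen or NSAIDs fell by at least 30%; Section 10.6(6) words the same idea as days per week. Section 10 gives no analysis window for the CIPN20. Section 10.2 plans multiple imputation under missing at random and a pattern-mixture sensitivity analysis.

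**The concern.** The diary is tied to study day and the visit is not, so a fully compliant early visit truncates the diary. Section 5.4 includes three CIPN measures in order to choose a phase III primary outcome, and it argues for the diary because averaging over a week may reduce variability. An early visit weakens only the diary in that comparison; a CIPN20 or TNAS completed at a single visit loses no entries.

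A rescheduled visit gives a score labelled Week 6 that reflects a longer exposure than the endpoint names. A participant who never returns leaves no post-baseline symptom score, even though a Week 4 diary finished by Day 28 may be sitting at home. The trial exists to supply efficacy estimates for a phase III design (Section 2.1), so data that could be kept cheaply are worth keeping.

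**Working it through.** **1. The plan's own figure.** Section 10.3 gives 126 evaluable for SMD 0.4, two-sided alpha 0.20 and 80% power. The standard formula gives 2 × (1.282 + 0.842)² / 0.4² = 56.4, so 57 per arm or 114 in all. The stated 126 is not reproduced; it gives about 83% power. That gap is conservative and separate from this point. For withdrawal, 126 / 0.85 = 148.2, or 149, close to the planned 150. The 15% allowance already covers participants who never return, so the stated power stands.

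**2. Evenings handed in.** Entries are made at bedtime, so the evening of the visit comes after hand-in. Evenings k = visit day − 35, with a maximum of 8 (Days 35-42 inclusive).

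**3. Illustrative precision.** Section 5.4 reports a pilot "standard deviation of 4.6 vs 5.7" for weekly averages against single-day ratings. Assume these are SDs of a score, with equal correlation between days. Then Var(mean of k evenings) = b + w/k, where w = (5.7² − 4.6²) / (1 − 1/7) = 13.22 and b = 5.7² − 13.22 = 19.27.

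| Visit day | Evenings k | Variance relative to k = 7 | Apparent change in days for a daily analgesic user, 7 days at baseline |
|---|---|---|---|
| 37 | 2 | 1.223 | −71% |
| 38 | 3 | 1.119 | −57% |
| 39 | 4 | 1.067 | −43% |
| 40 | 5 | 1.036 | −29% |
| 41 | 6 | 1.015 | −14% |
| 42 | 7 | 1.000 | 0% |
| 43-47 | 8 | 0.989 | +14% |

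- Visits uniform over Days 37-47: mean ratio 1.037, so the standard error rises by √1.037 − 1 = 1.8%.
- The early days average 1.092 and the rest 0.991. With 10% of visits early, 0.10 × 1.092 + 0.90 × 0.991 = 1.001; with 25% early, 1.016.
- If ANCOVA removes baseline variance at an assumed correlation r, the base becomes 21.16 × (1 − r²). The mean extra variance of 0.777 is then +4.9% (r = 0.5) to +7.2% (r = 0.7).

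**4. Analgesic classification.** The last column is k/7 − 1. With 2-4 evenings (visits on Days 37-39), a participant who takes analgesics every day crosses the 30% line purely through missing evenings. The baseline diary also varies: screening may fall on Day −9 to Day −4 (Section 5.3.1), giving 4-9 evenings. Raw day counts are therefore unequal at both ends.

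**5. Rescheduled visits.** Taking a month as 30 days, 42 + 30 = Day 72 (10.3 weeks), or 47 + 30 = Day 77 (11.0 weeks) if the missed appointment was booked for Day 47. In-window visits span 5.3-6.7 weeks. How often this will happen is not stated. If an assumed 2-10% were all seen at Day 72, the mean CIPN20 day would move from 42 to 42 + 0.02 × 30 = 42.6, up to 42 + 0.10 × 30 = 45.0.

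**6. Participants who never return.** 150 × 0.15 = 22.5, leaving 127.5 (pilot: 4 of 26, or 15.4%). If mail recovered an assumed 25%, 50% or 75% of these, 5.6, 11.3 or 16.9 scores would be added. The standard error would fall by 1 − √(127.5/133.1) = 2.1%, then 4.1% and 6.0%. This is an upper range, because it treats every withdrawal as reachable.

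**The case against.** The strongest reply is that the effect is small and the window ordinary. A ±5-day visit window and a rescheduling allowance are routine, and the one-month allowance trades timing for retention. Nothing says how many visits will be early or late, and no effect on the CIPN20 score itself is shown. All of this stands, and it is why the point is minor.

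Other parts also stand:

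- **Wrong outcome for the SDs.** 4.6 and 5.7 appear in the discussion of a composite, which is exploratory under Section 10.6(1). Section 10.5 analyses individual symptoms, whose pilot baseline SDs in Table 1 are 1.6-3.4. Their day-to-day variance is not given.
- **Recoverability.** The exits in Section 7.3 include death, withdrawal of consent and loss to follow-up, which mail mostly cannot repair.
- **Imputation.** It need not rest on baseline data alone. App usage and adverse-event information are gathered around the Day 7, 21 and 35 calls (Sections 5.3.7 and 8.3) and could serve as auxiliary variables.
- **Week recall.** Section 5.4 adds: "The participant will also be asked to rate these symptoms, while thinking about the past week at each visit". That form covers a full week even at an early visit, but Section 10.5 does not use it.
- **Silence.** Section 7.2 promises follow-up for endpoint data where possible, and the forms and appendices were not available. But that follow-up runs on the same visit schedule, and the 14-day data query in Section 9.1 is not a return route.

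Dropping the early side of the window would also repair the diary, since visits on Days 42-47 give 7-8 evenings. It would cost scheduling flexibility and would not help with missed visits.

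**Conclusion.** The point holds as a minor one. The 2-6 evening count is exact on the stated schedule, given evening entries and hand-in at the visit. The analgesic misclassification follows from it for visits on Days 37-39 against a seven-day baseline. A CIPN20 at about Day 72-77 is permitted, and no off-visit return is named in the text available.

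The size is modest: +22% variance at Day 37 and about +4% averaged over evenly spread visits. Both rest on composite SDs and an equal-correlation assumption, and the figure for the individual symptoms in Section 10.5 cannot be derived from the documents. The gain from mail is unknown; 2-6% on the standard error is an upper range.

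A reader might infer that the treatment estimate is biased or the trial underpowered. The documents do not support either. The rules are identical in both arms, so bias needs visit timing or attrition to differ by arm, and the sample size already allows for 15% loss. Nor do they support the idea that short diaries are worthless: on the same ratios, 2-3 evenings keep 1/1.223 = 82% to 1/1.119 = 89% of a full week's information.

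**What to change.** - **(a) Diary.** Run the Week 6 diary over the seven evenings before the booked visit, which also matches the past-week recall form. Write the start date on the diary and give a reminder before it starts. Keep all available entries; do not set short means to missing. If wanted, add a sensitivity analysis by number of entries.
- **(b) Missed visits.** For anyone who cannot attend within Day 42 ± 5, collect the CIPN20, the other patient-reported outcomes and both diaries on the same paper forms by mail within that window. Use that CIPN20 as the Week 6 value.
- **(c) Timing.** Add a sensitivity analysis excluding CIPN20 values taken outside Days 37-47.
- **(d) Analgesics.** In Sections 10.4 and 10.6(6), define reduction as the change in the proportion of recorded diary days with use.
- **(e) Exposure.** Reconcile the continued device use in Section 5.3.8 with the six-week exposure in Sections 5.2 and 7.1. Which should govern is for the sponsor to settle.

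The cost is a short amendment, mailing work and one extra reminder. The Day 35 call comes too late for early visits, and it should stay where it is because it carries the adverse-event check and usage report. Mailed forms may come back selectively. The diary will start before Day 35 for early visits (Days 30-36 for a Day 37 visit), a shift no larger than the visit window already allows. The window and the paper format are unchanged, and the Research Base already processes paper forms (Section 9.1).

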## 5.3.9. Follow-up phone call (Day 70 +/-5 days)

Coordinators will call participants and ask them whether they are using the commercial device.

## 5.4 Study Measures

The effects of the TENS intervention on CIPN symptoms and related functioning will be measured using patient-reported outcome (PRO) measures and functional assessments (see complete list below).

**Demographic and Clinical Information.** Demographic information will be obtained from all participants through the use of a standardized self-report questionnaire (i.e., **On Study** form). Variables to be assessed include age, height, weight, race, ethnicity, education, current work status, and occupation. Participants will also be asked to list all medications and treatments previously or currently used to treat their CIPN. Participants will also be asked if they have diabetes, edema, and commonly overlapping pain conditions, whether they drink alcohol, and if so, how much they consume weekly. Finally, they will be asked to rank how distressing typical CIPN symptoms are for them. The following clinical variables will be assessed via medical record review for all participants and recorded on the **Clinical record information form**: "neurotoxic cancer therapy (i.e., platinum, taxane, vinca alkaloid, bortezomib) (class, agent, date of last dose), type of non-study related chemotherapies, cancer diagnosis for which participant received the neurotoxic cancer therapy, history of chemotherapy other than study related chemotherapy (Yes/No and date of last dose), history of radiotherapy (past/current/No and date of last treatment), history of hormonal therapy (past/current/No and date of last dose)", history of alcoholism (Y/N), history of common overlapping pain conditions, current edema, and current medications that could affect CIPN.

#### Patient Reported Outcome Measures

**CIPN** will be evaluated in 3 ways in this learning phase study. The purpose of measuring CIPN in 3 ways is to identify the best measure to use as a primary outcome measure in a confirmatory trial. The European Organisation for Research and Treatment of Cancer-CIPN20 (EORTC-CIPN20) is one of the most commonly used measures of CIPN (i.e., legacy measure), however, it includes items that are focused only on the upper extremities that may not change in response to TENS administered on the lower limb as well as items that may not be highly specific to CIPN. The Treatment-Induced Neuropathy Assessment Scale (TNAS) is a relatively newer measure that has less data supporting its psychometric properties, but has well established content validity and does not include questions that are focused only on the upper limbs. Finally, the CIPN symptom inventory includes similar items to the 2 validated measures, but focuses solely on the lower limbs and sensory symptoms that we hypothesize will be modified by TENS. In addition, by administering it in a daily diary and averaging the ratings over 1 week at baseline and endpoint, as is the current practice in most chronic pain trials, variability in CIPN symptoms may be minimized, therefore increasing the assay sensitivity (i.e., ability of the measure to detect a true treatment effect) of the outcome measure. By including all 3 measures we will contribute to the validation of the newer measures and hopefully identify the measure that has the best assay sensitivity for measuring CIPN in the lower limbs. See below for further description of each measure.

(1) European Organisation for Research and Treatment of Cancer-CIPN20 (EORTC-CIPN20). The primary study outcome is CIPN as measured by the EORTC-CIPN-20.[54] The EORTC-CIPN20 includes items that assess CIPN-related symptoms and functional interference in daily activities. Multiple studies support the content and construct validity of the EORTC-CIPN20 [55-57] and it was identified as the best available PRO for CIPN at the NCI CIPN planning meeting.[14] (20-items)

(2) CIPN Symptom Inventory. Individual CIPN symptoms will be evaluated using weekly averages of daily diary 0 - 10 NRS scores [0 = no symptoms, 10 = worst symptom imaginable] of sensory symptoms

including hot/burning pain, sharp/shooting pain, tingling, cramping, and numbness (**Daily Diary**). The participant will also be asked to rate these symptoms, while thinking about the past week at each visit (**CIPN Symptom Inventory – week recall**). NRS scores and their composites are frequently used to assess symptoms in cancer and pain patients (e.g., MD Anderson Symptom Inventory [58]). Furthermore, the daily diary of a single-item 0–10 NRS for pain intensity is commonly used as the basis for approval of chronic pain medications by the FDA.[59] The symptom diaries will instruct the participants to focus on the symptoms in their lower limbs and perform ratings in the evening before bed while considering the past day. Based on our preliminary data, a composite measure of these symptoms in the lower limbs may be particularly responsive to the TENS intervention. Our pilot data also indicate that the outcome that is based on the average of the weekly symptom ratings has considerably less variability than the single day ratings (i.e., standard deviation of 4.6 vs 5.7) and could significantly decrease the sample size requirement of a future trial. **(5 items)** 

(3) Treatment-Induced Neuropathy Assessment Scale (TNAS). The TNAS is a PRO that assesses symptoms and functional interference from CIPN in 2 separate domains. It was developed and refined in multiple stages, including interviews with patients and clinicians to develop content valid items, and cognitive debriefing to assess the understandability of the items. It has acceptable reliability and sensitivity to change.[60, 61] (9 items)

**CIPN interference.** CIPN interference in general activity, mood, walking, normal work, relationships, sleep, and enjoyment of life will be measured using the **CIPN Interference Questionnaire**, which uses 0 – 10 NRSs [0 = does not interfere, 10 = completely interferes] adapted from the Brief Pain Inventory (BPI). [62] The BPI is a well-established measure used to assess chronic pain in clinical trials and clinically. **(7 items)** 

**Depression and anxiety.** Depression will be measured using the PROMIS-Depression Short Form 8A (**PROMIS 1**). Anxiety will be measured using the PROMIS-Anxiety Short Form 7A (**PROMIS 2**). PROMIS is a set of person-centered measures that evaluates physical, mental, and social health in the general population and those living with chronic conditions. The measures were developed with NIH funding using state of the art psychometric techniques and include brief measures that aim to maximize precision and brevity. [63] The Depression and Anxiety Short Forms have acceptable reliability and validity in several disease contexts. [64-67] In particular, they have demonstrated internal consistency, convergent validity with legacy measures, and sensitivity to change in a sample of cancer patients.[68] **(15 items)** 

**Physical function.** Physical function will be measured using the PROMIS-Physical Function Short Form 8b (**PROMIS 3**). In a large study of multiple clinical conditions, the PROMIS Physical Function measure was sensitive to change from interventions that would be accepted to improve physical function and was able to distinguish between groups of patients with different degrees of physical limitation. [69] In a cohort of almost 5000 cancer patients, multiple PROMIS Physical Function Short Forms showed high internal consistency and good convergent and discriminant validity.[70] **(8 items)** 

#### Single-Item Questions

(1) **Participant expectation questionnaire.** Participant expectation regarding the likelihood of TENS helping their CIPN will be assessed using a 1 – 5 likert-type scale. The question will be phrased as follows: "How likely do you think it is that a TENS device can improve your neuropathy symptoms?" [1= Not at all Likely, 3 = Somewhat Likely, 5= Very Likely].

(2) **Overall impression of change in neuropathy.** Impression of change in neuropathy symptoms will be measured using a single question (i.e., **General Impression of Neuropathy** form) that utilizes a 1 – 7 scale adapted from the patient global impression of change (PGIC). [71] The PGIC is commonly used in chronic pain trials to assess patient's experience of the change this beginning a treatment or clinical trial.[72]

(3) **Overall impression of change in activity.** Impression of change in ability to be active will be measured using a single question (i.e., **General Impression of Activity** form) that utilizes a 1 – 7 scale adapted from the patient global impression of change.[71] The PGIC is commonly used in chronic pain trials to assess patient's experience of the change this beginning a treatment or clinical trial.[72]

(4) **Blinding** will be assessed using the **Blinding Questionnaire** at the Week 6 visit by asking participants and blinded coordinators to guess which device the participant received and the basis for that guess (i.e., for participants, symptom relief vs. feel of the stimulation).

(5) **Changes in concomitant medications.** Participants will be asked if they changed any of their pain medications (other than acetaminophen or NSAIDs) throughout the study. This information will be captured on the **Changes in concomitant analgesic medications** form.

